### Specific Aims:

1. Test the effectiveness of a peer health coach intervention for improving health outcomes for Veterans with multiple CVD risks in a randomized controlled trial. The primary outcome is a reduction in systolic blood pressure (SBP) from baseline to follow-up at 1 year. Secondary outcomes include change in cardiovascular risk, as measured by the Framingham Risk Score, other cardiovascular risks (tobacco use, lipids) and health related quality of life. Using administrative data at 1 year following randomization, we will examine healthcare utilization, hospitalizations, and emergency room visits.
2. Assess the effects of a peer health coach intervention on intermediate outcomes that are intervention targets including social support, patient activation, *patient/provider communication* and health behaviors (e.g. medication adherence, physical activity, nutrition, *alcohol use, and stress management*).
3. Assess the cost of the intervention to inform feasibility for future studies.
4. Determine Veteran and staff satisfaction with the intervention and identify barriers and facilitators to adoption.

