### Study design overview:

We propose a randomized controlled trial to evaluate the effectiveness of **Vet-COACH**, a peer health coach program to control hypertension and reduce CVD risk among Veterans. The original program incorporated home visits by peer health coaches to deliver health education, counseling and goal setting support. Due to safety concerns and social distancing restrictions stemming from the COVID 19 pandemic, the program has transitioned to conducting all health coaching encounters, as well as enrollment and exit visits, via phone. This transition was implemented under IRB approval of the miscellaneous memo submitted at the beginning of the pandemic. These changes to conduct all health coaching encounters and exit surveys over the phone will be permanent for the remainder of the study. Our operations partners from NCP have developed extensive patient educational materials that will be used for the current study. We will train the peer health coaches to provide brief educational messages and link Veterans to existing clinical services at VHA, including their primary care PACT teams and community based programs. The main outcome will be a reduction in systolic blood pressure. Secondary outcomes are cardiovascular risk, as measured by the Framingham Risk Score (FRS), health care utilization and intermediate behavioral outcomes including patient activation, social support and health behaviors (e.g. diet and physical activity, medication adherence). *We will randomize a total of 200 individuals to the intervention group and 200 individuals to the control group.*

Our study design has limitations. Because of the nature of the intervention, we are unable to blind treatment assignment. The PI and [name] will provide overall supervision to the peer coaches. This model is necessary for program development. Because the intervention is being conducted at two sites, we are not proposing an economic evaluation to estimate cost-effectiveness, in part because such data would be of limited generalizability. Positive findings will lead to a larger multi-site trial that would include a cost-effectiveness analysis. These limitations are more than balanced by the strengths of this proposal. The proposed project is a prospective, randomized controlled trial that examines important outcomes with statistical power to detect clinically meaningful differences.

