**Follow-up calls for Intervention Group:**

The same peer health coach will make a total of 10 phone calls over the 12 month intervention period (Table 3), including 5 phone calls (to replace the previous home visits) plus 5 telephone follow up calls. We are basing the intervention frequency and number of visits on our previous work (1R18DK088072-01) and on frequencies noted in successful blood pressure trials. To increase generalizability of this model, we chose a minimal intervention necessary to review education topics and address important behaviors for all Veterans with hypertension. The peer health coach will support the participant in plan implementation at follow-up calls taking place 2, 4, 6 and 9 months after the initial call. Follow up telephone contacts are being used in our current study to maintain contact and support for participants.

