### Specific Aim 3: Determine intervention costs

These costs will include all labor and materials (pamphlets, home BP monitors, etc.) used in the intervention. We will administer weekly time sheets for all study personnel to estimate the amount of time they spend in various activities, and attribute the cost of these activities to either intervention costs or trial-specific costs, which are excluded from the intervention cost.

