### Barriers and facilitators to implementation

We will collect information on the barriers and facilitators of implementation. We include features in the study implementation to promote external validity such as inclusive enrollment criteria and using the minimum intervention needed for change (e.g. implementing with the minimum intensity we believe necessary for effectiveness). We will ascertain the degree of participation by eligible Veterans. We will use the following measures: (1) ability to contact potential participants (# reached/ # contact attempts); (2) study enrollment rate (#enrolled in study/ #eligible reached); (3) study participation rate (# with at least one follow-up home visit or participation in one project group activity/ # eligible reached); (4) program dropout rate (# discharged from program/ # participating in program); (5) study completion rate (# completing exit data collection/ # enrolled in study). The project manager will track feasibility by logging program costs, FTE used, space used, and logistical barriers encountered. Program staff will complete time study logs weekly during the first six months of the project and then for one week every quarter. The program manager will collect data on adaptability by logging changes in the research model protocols as the program is implemented. We will assess components that worked well or did not through participant satisfaction questions at the exit interview, and semi-annual discussions among project staff and investigators.

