Equivalence of participants in the intervention and control arms will be assessed on demographic and clinical variables, including outcomes, health status, co-morbidity, and utilization variables. Unadjusted comparisons between intervention groups will be calculated using t-tests and chi-square tests for continuous and categorical outcomes, respectively. Because this is a randomized controlled trial, no systematic bias is anticipated. However, we will conduct adjusted analyses and use as covariates those

factors that are thought *a priori* to be related to the primary and secondary outcomes. We will report summary statistics for all baseline covariates and outcomes (means, standard deviations, and quartiles for continuous variables; frequencies and percentages for categorical variables) by randomized group.

Cost of intervention

We will calculate intervention costs per patient. These costs will include all labor and materials (pamphlets, home blood pressure monitors, etc.) used in the intervention divided by the number of participants.

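### Aim 3 plans a single cost per patient although coaching moved from home visits to phone mid-trial; cost should also be shown by delivery mode

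*SAP*

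**What the plan says.** The Protocol (Specific Aims) gives the purpose of Aim 3: "Assess the cost of the intervention to inform feasibility for future studies". The SAP (section 6, Cost of intervention) states "We will calculate intervention costs per patient", with labor and materials "used in the intervention divided by the number of participants". The Protocol (section 5.6, Specific Aim 3) gives the same ratio. Neither splits it by delivery mode or period, and neither says whether participants means the coached arm or everyone randomised.

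Delivery changed during the trial. The Protocol's study design overview says: "The original program incorporated home visits by peer health coaches to deliver health education, counseling and goal setting support". After the pandemic began, "These changes to conduct all health coaching encounters and exit surveys over the phone will be permanent for the remainder of the study". The section on follow-up calls describes ten contacts, "including 5 phone calls (to replace the previous home visits) plus 5 telephone follow up calls". The SAP gives enrollment as 2017 to 2021, and its study summary still calls the intervention a home-visit programme.

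The Protocol describes three sources of staff time:
- Under Specific Aim 3: "We will administer weekly time sheets for all study personnel to estimate the amount of time they spend in various activities", with trial-specific time removed from the cost.
- Under Barriers and facilitators: "Program staff will complete time study logs weekly during the first six months of the project and then for one week every quarter".
- Under Measures, Specific Aim 1: logs of peer coach time, with no frequency stated.

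The SAP does not say which of these feeds the cost figure.

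**The concern.** A cost per patient is useful for planning only if it belongs to a programme that can be described. Someone budgeting a later trial needs either the cost of a course with five home visits or the cost of a course delivered entirely by phone. The planned ratio is a weighted average of the two, with weights set by when the pandemic interrupted enrollment. It could not be carried over to either design without knowing those weights and the two underlying costs.

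The SAP recognises elsewhere that the change matters. It plans separate analyses of primary and secondary outcomes for 12-month data collected before and after the onset of COVID, and a sensitivity analysis of the remote phase. Cost, which delivery mode can change directly through travel and contact time, has no such split.

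Only the usefulness of Aim 3 is at stake. No hypothesis test depends on it.

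**Working it through.** **Plan's own figure.** There is none to reproduce. The documents give no cost, no hours per contact and no home/phone split. That both modes are pooled is inferred from the single ratio and the absence of any split.

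**Inputs from the documents.** Ten contacts, five of which changed mode (Protocol, Follow-up calls for Intervention Group). Arms of 200 and 200 (Protocol, Study power and sample size). A 4-year study (Protocol, Objectives).

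**Assumed inputs.** h is the share of coached participants whose coaching was by home visit. R is the home/phone ratio of full cost per participant.

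**Step 1: effect of pooling.** Pooled cost = h × home cost + (1 − h) × phone cost. Dividing by phone cost gives 1 + h(R − 1):

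| h | R = 1 | R = 1.25 | R = 1.5 | R = 2 | R = 3 |
|---|---|---|---|---|---|
| 0.25 | 1.00 | 1.06 | 1.13 | 1.25 | 1.50 |
| 0.50 | 1.00 | 1.13 | 1.25 | 1.50 | 2.00 |
| 0.75 | 1.00 | 1.19 | 1.38 | 1.75 | 2.50 |

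Dividing by R instead gives pooled cost relative to home cost. At R = 1.25 this runs from 1.0625/1.25 = 0.85 to 1.1875/1.25 = 0.95. At R = 3 it runs from 1.5/3 = 0.50 to 2.5/3 = 0.83.

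**Step 2: what R demands.** Only five of ten contacts changed. Suppose every call costs 1 unit and a home visit costs r units. Then, for contacts alone, R = (5r + 5)/10, so r = 2R − 1. R = 1.25 needs r = 1.5, and R = 3 needs r = 5. Costs common to both modes (training, supervision, participant items) push the required r higher, so the top of the table is demanding.

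**Step 3: denominator.** If the divisor were all 400 randomised participants instead of the 200 assigned to coaching, the figure would halve: 200/400 = 0.5.

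**Step 4: time source.** Over 4 years (208 weeks), weekly sheets give 208 logged weeks. The schedule under Barriers and facilitators gives 26 + 14 = 40 weeks, or 19%. Of these, 26/40 = 65% fall in the first six months, which are 26/208 = 12.5% of the project. After that, 14 of 182 weeks are logged (7.7%). If these logs were the cost source, the phone phase would be sampled at about one week in thirteen, and an unweighted average would lean towards the start-up period.

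**The case against.** The strongest case against acting is that Aim 3 is descriptive. The Protocol disclaims a cost-effectiveness evaluation, and half the contacts were telephone calls from the outset. Shared costs pull R towards 1. Phone delivery may also add costs, such as mailed monitors and scales where these count as intervention cost, so even the direction is not certain. All of this stands. It limits the severity but does not supply the missing split.

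Three stronger readings are tempting and are not supported.

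- A reader might infer that the two time-recording schedules contradict each other. They differ in name (time sheets; time study logs), in staff (all study personnel; program staff) and in purpose (Aim 3 costing; feasibility), so they may be two instruments. The weekly sheets are the ones described under the Aim 3 heading. On that schedule the start-up over-weighting in Step 4 does not arise, and coach logs and encounter forms also cover the phone phase. What stands is that the SAP names no source.
- A reader might put a firm figure on the overstatement, from assumed visit lengths and travel times or from assumed heavier start-up effort. The documents give none of these inputs, and a calculation from coach hours alone omits other labor and materials. Nor does any passage propose an unweighted average of logs.
- A reader might conclude that the figure describes a programme nobody will run. The Protocol makes phone delivery permanent only for the rest of this study and does not name the mode of any later trial.

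**Conclusion.** The point holds as a minor one. As written, Aim 3 yields one average over home-visit and phone coaching, which serves its planning purpose poorly. The size is undetermined: pooled cost is 1.06 to 2.5 times phone cost over the assumed ranges (h 0.25 to 0.75, R 1.25 to 3), equals it if R = 1, and falls below it if R is less than 1. The undefined denominator and the unnamed time source are missing details to settle in the same edit. The primary blood pressure comparison is unaffected.

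**What to change.** Amend the Protocol (section 5.6, Specific Aim 3) and the SAP (section 6, Cost of intervention) as follows.

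1. Report cost per participant randomised to coaching separately for home-visit and phone delivery, beside the pooled figure. Define the denominator in those terms.
2. Allocate labor and materials to a mode by encounter or by calendar period, using the coach time logs and the encounter forms. A participant whose 12 months straddle the switch then contributes to each mode. With calendar allocation, that participant counts in each denominator for the fraction of the 12 months falling in that phase.
3. Show costs common to both modes, such as initial coach training, on a separate line. Otherwise start-up cost is attributed to home visits merely because they came first.
4. State that the weekly time sheets are the Aim 3 time source. If the logs described under Barriers and facilitators have to be used instead, weight each log by the calendar time it represents.

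The cost is some wording and two subtotals, which the coach logs and encounter forms should support without new data collection. Each mode's figure rests on fewer participants and is less precise. Mode also remains tied to calendar time, so the two figures should be presented as descriptions and not as a comparison of modes.
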